### 9.5 Handling of Missing Data

Missing data will not be imputed.

### 9.6 Multiplicity

In the primary analysis, multiplicity will not be an issue since there is only one primary endpoint. For the 2 secondary endpoints, the hypotheses will be tested in the pre-specified order only if the superiority is demonstrated in the primary analysis. Therefore, the type I family-wise error (FWE) for the total of 3 hypothesis tests (primary analysis (once) and secondary analysis (twice)) is controlled (one-sided 2.5%). [REDACTED]

[REDACTED]

### 9.7 Safety Analysis

Lists of untoward safety events occurring from consent to before cataract surgery will created. The incidences and proportions of adverse events and deficiencies occurring after cataract surgery will be calculated by surgical technique.

## 9.8 Sample Size Justification

The 50 evaluable subjects will be enrolled for this study. For CDE, treatment difference was assumed 1.9% with common standard deviation of 1.2%. The sample size was simulated in Table 1 varying correlation coefficient between both eyes because intra-subject positive correlation between both eyes is assumed for endpoints in this study.

Table 9.8-1 Statistical Power for CDE (N=50)

Correlation between Both Eyes	Actual Power
0	>0.999
0.25	>0.999
0.50	>0.999
0.75	>0.999
0.99	>0.999

Also, for ECD, treatment difference and common standard deviation of ECD percent change from Baseline at Visit 5 was assumed 5.5% with common standard deviation of 11%. The sample size was simulated in Table 2 in the same manner as CDE.

Table 9.8-2 Statistical Power for ECD (N = 50)

Correlation between Both Eyes	Actual Power
0	0.688
0.25	0.808
0.50	0.934
0.75	0.998
0.99	>.999

Considering 8% dropout rate, 55 subjects will be enrolled for this study.

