### 4.3 Exclusion Criteria

Exclusion criteria (Prior to Surgery)

Patients meeting any of the following 1)-16).

- 1) Corneal opacity that would interfere with the laser beam
- 2) Hypotony or the presence of a corneal implant
- 3) Residual, recurrent, active ocular or eyelid disease, including any corneal abnormality (for example, recurrent corneal erosion, etc.)
- 4) Corneal disease that precludes appplanation of the cornea or transmission of laser light at 1030 nm wavelength
- 5) Descemetocoele with impending corneal rupture
- 6) Presence of blood or other material in the anterior chamber
- 7) Poorly dilating pupil, such that the iris is not peripheral to the intended diameter for the capsulotomy
- 8) Conditions which would cause inadequate clearance between the intended capsulotomy depth and the endothelium
- 9) Any contraindication to cataract
- 10) Corneal endothelial cell density is less than 2000 cells/mm^2
- 11) Presence of peripheral iridotomy
- 12) Patients whose cataract grade of both eyes are two different levels
- 13) Pregnancy current or planned during the course of the study
- 14) Any subject currently participating in another investigational drug or device study that may confound the results of this investigation
- 15) Subjects who are expected to require an ocular surgical treatment at any time during the study

(other than Nd:YAG capsulotomy)

- 16) Disqualified by the investigator or the sub investigator because of systemic or ophthalmic diseases

[Rationale for the exclusion criteria]

1)-9): contraindication/prohibition of the test device

10) and 11): To avoid factors potentially affecting the secondary efficacy endpoints

12): To avoid the risk of creating a difference in background of both groups

The other criteria were established for general safety consideration.

Exclusion criteria (During Surgery)

Patients whose study eye meets any of the following 1)-6).

- 1) Eyes with any other additional procedures during the cataract surgery and IOL implant due to intraoperative complications that required further intervention (including but not limited to posterior capture rupture, vitreous loss, etc.)
- 2) Incomplete CCC by LenSx
- 3) Significant anterior chamber bleeding
- 4) Uncontrolled intraocular pressure
- 5) Bag-sulcus, sulcus-sulcus or unknown placement of the haptics
- 6) Disqualified by the investigator or the sub investigator because of any clinical reason (adverse event etc.)

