##### 9.4.1.2 Analysis methods

The descriptive statistics of CDE at Visit 00 (surgery day) will be calculated for each of the surgical techniques (arithmetic mean, standard deviation, N, median, minimum and maximum) and the means will be estimated using 95% confidence intervals based on the MMRM (mixed model for repeated measures). The superiority of LenSx to Conventional will be tested if there is a significant difference in mean between the surgical techniques (MMRM-based t-test, significance level: one-sided 2.5%).

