#### 【臨床成績】

白内障患者を対象として米国にて臨床試験を1試験実施した。白内障手術手技のうち、前囊切開、水晶体分割、角膜切開について、片眼は本装置を用いて（レーザー群）、対側眼は従来の手技を用いて（マニュアル群）手術を実施した。なお、本試験で用いた本装置の各設定値の範囲は、前囊切開の切開径4.2～5 mm、水晶体分割の分割数はチョップパターン2～3（切開径4.2～4.7mm）、シリンダーパターン1～4（切開径2.5～4.5mm）、水晶体分割のオフセット値は前房側500 $\mu$ m、後房側800 $\mu$ mであった。白内障手術を受けた65例がITT解析の対象となった。レーザー群の65例全例においてSoftFit患者インターフェースの圧平が成功した。レーザー群65例のうち64例に本装置による前囊切開、水晶体分割を実施し、全例が前囊切開と水晶体分割の完全例であった。また、レーザー群の65例に本装置を用いた角膜切開を実施し、メイン創口切開とサイドポート切開で部分的にブレードによる切開が必要となったそれぞれ4例（6.2%）を除いて、いずれも完全例であった。

本装置による前囊切開の真円度は、レーザー群で $0.8978 \pm 0.0048$  (平均値  $\pm$  標準偏差, 以下同様)、マニュアル群で $0.8875 \pm 0.0079$  であり、マニュアル群と比較して平均値、標準偏差ともに差がみられた (対応のある t 検定  $p < 0.0001$ , Pitman の検定  $p = 0.0004$ )。一方、前囊切開のサイズは 5mm の設定に対して、レーザー群で $4.9780 \pm 0.1909$ mm、マニュアル群で $4.9828 \pm 0.4624$ mm であり平均値に差 (対応のある t 検定  $p = 0.7160$ ) は認められなかったが、レーザー群の標準偏差はマニュアル群に比し小さかった (Pitman の検定  $p < 0.0001$ )。

白内障のグレード別の超音波時間は、白内障のグレードが「硬い」でレーザー群が $40.5 \pm 26.1$ 秒、マニュアル群で $50.8 \pm 13.1$ 秒であり大きな差が認められた (対応のある t 検定  $p = 0.0140$ )。また、白内障のグレード別の CDE では、「中等度」でレーザー群が $6.170 \pm 2.757$ 、マニュアル群で $7.242 \pm 2.159$ であり、「硬い」でレーザー群が $8.666 \pm 5.119$ 、マニュアル群が $10.749 \pm 4.487$ であり大きな差が認められた (対応のある t 検定  $p = 0.0378$ ,  $p = 0.0194$ )。

臨床試験で確認されたもっとも浅い前房深度は 2.53mm であった。

なお、本装置との因果関係が否定できない有害事象及び不具合は認められなかった。

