## Appendix C Selection of Surgeon

[figure not shown]
[figure not shown]
Regarding combination of LenSx and Centurion (hereafter called LenSx group) and conventional cataract surgery (hereafter called Conventional group), the surgeons of this study surgery will be decided as follows.

Surgeon A and Surgeon B should be the same person respectively for all surgery of this study.

Group	Surgical Procedure	Surgeon
LenSx	Anterior capsulotomy and lens fragmentation by LenSx	Surgeon A
	Surgical procedure after the above mentioned procedure	Surgeon B
Conventional	All of the surgical procedure	Surgeon B

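### Does the assumed CDE standard deviation of 1.2, lower than any in Appendix B, undermine the stated primary power of >0.999?

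*Protocol*

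**What the plan says.** The CDE assumption in Protocol 9.8, repeated in SAP 7, reads "For CDE, treatment difference was assumed 1.9% with common standard deviation of 1.2" per cent. The number of pairs is fixed first: "The 50 evaluable subjects will be enrolled for this study". Protocol Table 9.8-1 and SAP Table 7-1 then give power above 0.999 at correlations of 0, 0.25, 0.50, 0.75 and 0.99. Only the correlation varies. No origin is given for 1.9 or 1.2, and SAP section 8 lists no references.

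The test is set in Protocol 9.4.1.2: "MMRM-based t-test, significance level: one-sided 2.5" per cent. CDE is the only primary endpoint and opens the way to ECD and then torsional amplitude. Under Protocol 9.6, for the two secondary endpoints, "the hypotheses will be tested in the pre-specified order only if the superiority is demonstrated in the primary analysis".

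The only CDE data in either document are in the clinical-results section of the package insert (Protocol Appendix B), as mean ± SD:

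| Grade | Laser eye | Manual eye | Difference | Paired-t p |
|---|---|---|---|---|
| Moderate | 6.170 ± 2.757 | 7.242 ± 2.159 | 1.072 | 0.0378 |
| Hard | 8.666 ± 5.119 | 10.749 ± 4.487 | 2.083 | 0.0194 |

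**The concern.** A power table that reads >0.999 in every row tells the reader little, because the input that matters most, the SD, is never varied. The one set of CDE figures in the documents has SDs from 2.159/1.2 = 1.8 to 5.119/1.2 = 4.3 times the planned value. That trial used other laser patterns, but this cannot account for the two manual-arm SDs, 2.159 and 4.487, which are also above 1.2. The present trial also pools Emery-Little Grades 2 to 4, which widens the spread between subjects.

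At stake is the gate. If CDE power were well below 1, the ECD powers in Table 9.8-2 would overstate the chance of a confirmatory ECD result. With CDE power of 0.877 and ECD power of 0.934 (correlation 0.50), that chance is at most 0.877. It is 0.877 × 0.934 = 0.82 if the two tests are independent.

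**Working it through.** **1. The plan's own figures.** For n pairs, per-eye SD s and correlation r, SD_diff = s√(2(1 − r)). The noncentrality is d√n / SD_diff on 49 degrees of freedom, at one-sided 0.025.

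- CDE, d = 1.9, s = 1.2, r = 0: SD_diff = 1.2 × √2 = 1.697, noncentrality = 1.9 × 7.071 / 1.697 = 7.92, power >0.999. Larger r only raises it.
- ECD, d = 5.5, s = 11: power 0.688, 0.808, 0.934, 0.998 and >0.999, exactly as printed.

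Both tables reproduce. The ECD match also shows that the common SD in these tables is per eye, so 1.2 can be set beside the Appendix B SDs, assuming the same CDE scale (Protocol 9.8 writes a per cent sign, Appendix B does not).

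**2. Power if Appendix B's per-eye SDs applied.** With unequal arm SDs, SD_diff² = s₁² + s₂² − 2r·s₁s₂. At n = 50 and d = 1.9:

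| SDs used | r = 0 | 0.25 | 0.50 | 0.75 |
|---|---|---|---|---|
| Moderate (2.757, 2.159) | 0.964 | 0.991 | 0.999 | >0.999 |
| Hard (5.119, 4.487) | 0.490 | 0.607 | 0.778 | 0.969 |

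The hard row would describe a trial of hard cataracts only, which this is not. Its left-hand columns also assume little correlation between fellow eyes. The plan requires matched grades, since it excludes "Patients whose cataract grade of both eyes are two different levels". So pooling grades raises the correlation as well as the SD.

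**3. A mixed population, using the paired information in Appendix B.** The reported p-values imply SD_diff = d√m / t, where m is the number of patients in the grade and t is the two-sided critical value for that p. Appendix B does not give m, so it has to be assumed. For a hard share w, the mixed variance is (1 − w)·s_m² + w·s_h² + w(1 − w)(2.083 − 1.072)². Worked case with m = 20 in each grade and w = 0.5:

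- Moderate: 1.072 × √20 / 2.233 = 2.15.
- Hard: 2.083 × √20 / 2.554 = 3.65.
- Mixed: √(0.5 × 2.147² + 0.5 × 3.648² + 0.25 × 1.011²) = 3.04.
- Noncentrality: 1.9 × 7.071 / 3.035 = 4.43, power 0.991.

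Other assumed sizes, with w = 0.5 and d = 1.9:

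| m (moderate, hard) | SD_diff, mixed | Power |
|---|---|---|
| 15, 15 | 2.56 | 0.9993 |
| 20, 20 | 3.04 | 0.991 |
| 30, 30 | 3.81 | 0.933 |
| 25, 40 | 4.22 | 0.877 |

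The last row is the least favourable pair with 20 to 40 per grade and at most the 65 patients of that trial. Power of 0.999 at d = 1.9 needs SD_diff of 2.61 or less.

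**4. Other assumptions, with 20 to 40 per grade.** With a quarter hard, power at 1.9 is 0.97 to 0.999. With three quarters hard it is 0.77 to 0.97. At Appendix B's own mixed difference, (1.072 + 2.083)/2 = 1.58, the half-and-half mix gives 0.74 to 0.95.

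**The case for a change.** The best case for acting is that the documents contain one empirical benchmark, every SD in it exceeds 1.2, and nothing in the documents supports a fall to 1.2. An ethics committee reading section 9.8 would take the primary test as certain to succeed, and could not see that the ECD powers leave the CDE gate out of account. The remedy is cheap: cite a source, add a row with a larger SD, drop the per cent sign, and add a sentence on the gate.

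The comparison of SDs stands, and so does the missing source. Two parts do not carry through.

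First, Appendix B is a weak yardstick. It is device labelling for a different trial. It used chop and cylinder patterns, states no phaco system or settings, gives no patient numbers per grade, and has hardness labels not mapped to Emery-Little. An unstated phaco system or settings could widen both arms, manual included. The present trial fixes the phaco machine and its settings, and Appendix C holds the operators constant: "Surgeon A and Surgeon B should be the same person respectively for all surgery of this study". A smaller spread is plausible, though no figure in the documents puts it at 1.2.

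Second, the gate argument uses the least favourable figure. At 20 patients per grade the product is 0.991 × 0.934 = 0.93, almost the printed 0.934. Table 9.8-2 is headed as power for ECD, which is ordinary power for a single test, and Protocol 9.6 states the gate openly.

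**Conclusion.** No change follows. The power tables are right for their stated inputs. The real gap is that 1.9 and 1.2 have no source and the SD is not varied. With Appendix B's spread, a half-and-half grade mix and a difference of 1.9, power is about 0.88 to above 0.999. It falls below 0.80 only under further assumptions: mostly hard cataracts with unfavourable per-grade numbers, or a smaller true difference such as 1.58 at the unfavourable end of the range. Those per-grade numbers, the grade mix and the mapping of hardness labels are all assumed, so these figures show sensitivity to the SD and do not show a shortfall.

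A source or a further row would also decide nothing. The planning SD does not enter the analysis: the mixed model in SAP 4.3 estimates its variances from the trial data, so the 2.5% error rate does not depend on 1.2. At the stated inputs ECD, not CDE, is the endpoint with limited power (0.688 to 0.934 for correlations from 0 to 0.50). The sample size, test, significance level and testing order would all stay as they are. The per cent sign on CDE is a clerical slip with no effect on power.

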## 10 ADVERSE EVENTS AND DEVICE DEFICIENCIES, etc.

### 10.1 General Information

Refer to the Glossary of Terms below for categories of Adverse Experiences, AEs and SAEs.

#### Adverse Experience:

Any untoward medical occurrence, unintended disease or injury, or untoward clinical signs (including abnormal laboratory findings) in subjects from consent to before cataract surgery will be recorded.

#### Adverse Event (AE):

Any untoward medical occurrence, unintended disease or injury, or untoward clinical signs (including abnormal laboratory findings) in subjects after cataract surgery (including during cataract surgery), users or other persons, whether or not related to the investigational medical device (test article). *For subjects, this definition includes events related to the test article or the procedures involved. For users or other persons, this definition is restricted to events related to the test article.*

#### Serious Adverse Event:

Adverse event that led to any of the following, or that needed treatment not to lead to the following results:

- Death.
- A serious deterioration in the health of the subject that either resulted in:
  - a) a life-threatening illness or injury.

*Note: Life-threatening means that the individual was at immediate risk of death from the event as it occurred, ie, it does not include an event which hypothetically might have caused death had it occurred in a more severe form.*

- b) any potentially sight-threatening event or permanent impairment to a body structure or a body function.

- c) in-patient hospitalization or prolonged hospitalization.

*Note: Planned hospitalization for a pre-existing condition, without serious deterioration in health, is not considered a serious adverse event. In general, hospitalization signifies that the individual remained at the hospital or emergency ward for observation and/or treatment (usually involving an overnight stay) that would not have been appropriate in the physician's office or an out-patient setting. Complications that occur during hospitalization are adverse events. If a complication prolongs hospitalization or fulfills any other serious criteria, the event is serious. When in doubt as to whether "hospitalization" occurred, the event should be considered serious.*

- d) a congenital anomaly/birth defect,

- e) a medically important event or reaction.

#### Non-serious Adverse Event

Adverse event that does not meet the criteria for a serious adverse event.

#### Adverse Device Effect (ADE)

Adverse event related to the use of an investigational medical device (test article).

*Note: This definition includes adverse events resulting from insufficient or inadequate instructions for use, deployment, implantation, installation, or operation; any malfunction; and use error or intentional misuse of the test article.*

### Serious Adverse Device Effect (SADE)

Adverse device effect that has resulted in any of the consequences characteristic of a serious adverse event.

### Device Deficiency

Inadequacy of a medical device with respect to its identity, quality, durability, reliability, safety, or performance.

### Safety Information:

Information about quality, efficacy and safety for medical device and information which is needed for appropriate use, including:

- Use error
- Abnormal Use
- Product tampering
- Product counterfeiting
- Product theft

## 10.2 Procedure for Reporting of Serious Adverse Events (SAE)

The investigator will report the serious adverse event or the risk of causing serious adverse event to Alcon within 24 hours after confirming the event.

After obtainment of detailed information on the serious adverse event, the investigator will prepare a report and immediately submit it to Alcon and the head of the medical institutions.

When the SAE is correspond to “Death or a life-threatening ADE” or “Serious and unexpected ADE other than Death or a life-threatening event”, the sponsor will immediately notify them to heads of all medical institutions and all investigators by document.

## 10.3 Report of Adverse Events and Evaluation of the Causal Relationship

All adverse experiences from consent to before cataract surgery and adverse events after signed informed consent will be documented on the Adverse Event Case Report Form (CRF).

For every AE, the investigator will assess the casual relationship of the medical device at “related” or “not related”.

## 10.4 Intensity Assessment of Adverse Events

For every AE, the investigator must assess the intensity (severity). Events should be classified as mild, moderate, or severe. These classifications should be based on the following definitions:

Intensity:

- |          |  |
|----------|--|
| Mild     | An AE is mild if the subject is aware of but can easily tolerate the sign or symptom.  |
| Moderate | An AE is moderate if the sign or symptom results in discomfort significant enough to cause interference with the subject's usual activities. |
| Severe   | An AE is severe if the sign or symptom is incapacitating and results in the subject's inability to work or engage in their usual activities. |

## 10.5 Follow-up of Subjects / Subjects with Adverse Events

In the event of acknowledging any adverse events, the investigators should immediately take appropriate actions irrespective of the presence or absence of causal relationship with the test article. And the investigators will make a follow-up of the adverse event if it is possible. When the subject needs medical treatment, the investigators should inform the subject of the matter. For subjects who are experiencing ongoing unresolved adverse events at the time of their study completion or early discontinuation from the study, it is recommended that the investigator schedule an appropriate follow-up visit in order to determine the outcome of the event.

## 10.6 Subject Pregnancy

Women ██████ planning to become pregnant during this study period or women who are pregnant at the time of study entry are excluded from participation.

## 10.7 Provision of Safety Information

Investigators provide safety information which is needed to make a detailed report on demand from the sponsor.

# 11 ETHICS

## 11.1 Independent Ethics Committee

Prior to the start of the study, the Independent ethics committee (IEC) of each participating institution is required to inspect and evaluate the planned study as to the acceptability of implementing the study, appropriateness of the contents of the protocol, case report form, questionnaire and informed consent document, and other matters related to the study from the ethical, scientific and medical points of view, with an ultimate goal of protecting the human rights and welfare of the subjects.

The inspection and examination by the IEC may be performed again also during a certain period of time after the start of the study or when the head of the participating institution sees the necessity of additional inspection/examination so that the study may be monitored continuously.

## 11.2 Ethical Consideration

The study is implemented after a contract on implementation of the study is concluded between the Sponsor and each participating institution following inspection and authorization of the study by the IEC of each participating institution.

If deemed necessary to ensure safe implementation of the study, the protocol of this study may be revised in accordance with the provisions set forth in “Section 12. PROTOCOL AMENDMENTS”.

This study is carried out in accordance with the principles set forth in the Declaration of Helsinki and the protocol. This study will be conducted in accordance with GCP and Ethical Guidelines for Clinical Studies (2014, Ministry of Education, Culture, Sports, Science and Technology and Ministry of Health, Labour and Welfare Notification No.3), in principle.

## 11.3 Protection of Subjects' Privacy

To protect the privacy of individual subjects, only identification codes is used to represent the subjects whose data are used in case reports, etc., so that leakage of the identifiable individual information about the subjects can be prevented.

## 11.4 Specifications to Secure Safety of Study Subjects

### 1) Actions to take for adverse events

In the event of acknowledging any adverse events, the investigator or the subinvestigator should immediately take appropriate actions irrespective of the presence or absence of causal relationship with the test article.

### 2) Supply of new information

In the case of obtaining safety-related new and significant information related to the clinical trial, the sponsor should supply the information in writing to the investigator and the subinvestigator and the head of the study site and take necessary actions.

### 3) Avoiding emergent risks

In the event of deviating from the study protocol to avoid the emergent risk and secure safety of the study subject or because of other unavoidable clinical reasons, the investigator will retain the record and submit the documentation and justification of the protocol deviation to the sponsor and the head of the study site.

## 11.5 Compensation for Health Hazards

If any subject has sustained health hazards arising from this study, best healthcare is provided to that subject. The Sponsor needs to be covered by insurance for liability arising from clinical trial.

## 16 CONFIDENTIALITY AND PUBLICATION OF STUDY

All information related to this clinical study including the protocol and therapeutic results are the property of the sponsor, and the investigator and other medical staff engaged in the clinical study must keep such information confidential.

The sponsor can submit the results of this clinical study to the health authority and use the results as “Information on Proper Use” of the product. Sponsor will register the summary of the study to open database (The Database Center of the National University Hospitals, JAPIC Clinical Trials Information, or JMACCT Clinical Trials Registry, etc.) before conducting the study, and will properly update it based on the revision of the protocol or study progression.

When publishing the results of this clinical study in the congresses or medical journals, the investigators and other medical staff must obtain prior approval from the sponsor. The sponsor can confirm the contents of presentation beforehand.

After completion of the study, sponsor and the investigators will report the result of the study after taking necessary steps for protecting the right and benefits of the subjects, related persons, sponsor, investigators, and so on.

